6. Follow-up calls/visits: a research team member will call the mother of the baby once they have been discharged home, if the baby is discharged prior to Day 15 of their life. We want to follow up on the babies and learn how they are doing and make sure they are not going into "Delayed" NAS. For babies who are discharged early it is more likely they could go into delayed NAS and that is why we plan to call the mothers daily, for up to 10 days after the baby takes their last dose of study medication, to ask about their baby's status. We are interested in how the baby is feeding, are they breast or bottle feeding the baby, what is the baby's mood (crying excessively, fussy, agitated), sleeps for how many hours after feeding, sneezing a lot, sweating, vomiting, gaining weight, loose stools or watery stools, etc. We also need to ask the mother all the medications she is taking, if she is breastfeeding her baby, since we know these medications will enter the baby's system through the breast milk. If a baby is not discharged before day 15 of their life, the research team member will visit the baby in the hospital daily, for 10 days after their last dose of study drug, to check on the status of the baby from the clinical team caring for the baby. If the mother is home while the baby remains hospitalized, the research team member will also call the mother on a daily basis to maintain contact and to ask the mother all the medications she is taking if she is breastfeeding her baby (we know these medications may enter the baby's system through the breast milk).

7. The final follow-up call (or visit if the baby is still in the hospital) will occur approximately 30 days after the baby's last dose of study medication; this call (or visit) will be to determine if any previously reported adverse events have resolved and/or if any new adverse events have occurred since the last follow-up call or visit.

The primary endpoint will be the incidence of NAS in enrolled neonates and will be measured by the need for pharmacologic treatment for the symptoms of NAS (Morphine). The secondary endpoint of the severity of NAS will be measured by the length of the hospitalization (birth to discharge), the total dose of narcotic required to treat the symptoms of NAS, and the need to include barbiturates in the treatment of symptoms of NAS.

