5.0 Potential Risks

Potential Risks
Ondansetron

Potential Risks	
To Mother	Well-studied in adults and considered safe Routinely given to pregnant women in first trimester for hyperemesis gravidarum and during labor as antiemetic Routine doses used in this protocol minimize risks to the mother
To Fetus	Classified as pregnancy class B (not shown to cause teratogenicity in animal studies and not well-studied in humans) Commonly used clinically in labor and delivery to treat maternal nausea, thus exposing the fetus transplacentally Considered to have minimal risk to the fetus
To Neonate	Not well-studied in this age group Used clinically to treat postoperative nausea in infants and young children and considered to carry minimal risk One double-blinded, randomized, controlled trial compared ondansetron to placebo for preventing postoperative emesis in 1-24 month olds (#22). No differences were found in number or pattern of adverse events between groups
Delayed onset of NAS	
To Mother	Not applicable
To Fetus	Onset of NAS symptoms may be delayed as a result of ondansetron treatment Given the prolonged effects of methadone, the late-onset risk may be particularly relevant to patients on methadone
To Neonate	If neonates do not demonstrate symptoms of NAS prior to discharge from the hospital; parents will be instructed to closely observe for symptoms when home and told to either call their baby's doctor or take their baby to their pediatrician if the baby is showing signs of NAS
Phlebotomy	
To Mother	Minimal risk Approximately 5 cc (one teaspoon) maximum of blood will be drawn from the mother by needle stick or she can have a finger stick if the site uses the filter paper to obtain dried blood spots. Rare side effect is hematoma and/or infection
To Fetus	Not applicable
To Neonate	Study drug will be administered to the neonate either orally or via standardized intravenous infusion (IV) technique for this population, posing no additional risk
Heel Stick	
To Mother	Not applicable
To Fetus	Not applicable
To Neonate	Do heel stick to collect 1-3 drops of blood at least twice after delivery only if blood not collected for clinical reasons in the first 12 hours after birth Minimal risk of hematoma or infection
Electrocardiogram	

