To Neonate Risk is no greater than placebo risk To minimize risk, screen for QT prolongation and give dose (determined in Aim 1) to reach blood level predicted to have desired clinical effect Dose will be within dose limits studied in slightly older infants (less than 0.15 mg/hr in 12hours) Duration of exposure will be minimized by stopping study drug after a maximum of five days of study drug treatment, Will be discontinued if related adverse events occur If QTc interval abnormalities occur or a neonate has QTcB greater than or equal to 480 ms, the neonate's study drug will be stopped and no further dosing will occur; follow up 'safety' EKGs will be done until the QTc has returned to 479ms or less, if possible. All neonates will have a screening ECG prior to their first dose of study medication & an ECG after each dose for a maximum of 6 ECGs in 5 days.
Delayed onset of NAS
To Mother Not applicable
To Fetus Risk will be managed by educating the parents about the NAS symptoms Provide parents with contact information for both their clinical caregivers and the research team Ask parents to report delayed onset to both groups Appropriate medical care will be provided Parents may receive a maximum of 10 daily follow-up telephone calls if the baby is discharged before Day 15 of life; the calls are being done to review continuation or recurrence of NAS symptoms and the occurrence of other adverse events. The research staff will call daily, through a maximum of 10 days after the last dose of study drug. If the baby is still in the hospital through Day 15 of life, this information will be gathered by the research staff visiting the neonate in the hospital. The final follow-up phone call to the parents will occur approximately 30 days after the baby's last dose of study medication to check for any occurrence of new adverse events and to inquire about the resolution of any previously reported adverse events.
To Neonate Not applicable
Phlebotomy
To Mother Minimize risks of hematoma and infection by following all hospital guidelines including using aseptic technique and applying pressure to site after sample collection Only qualified personnel may collect blood samples for analysis
To Fetus Not applicable

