The meetings will be divided into three sessions: open, closed, and executive. During the open session, [name] will present relevant information about the trial including the following: 1) number of subjects enrolled, 2) problems with data accrual or follow up, 3) baseline demographic data, 4) compliance issues, 5) frequency of adverse events, 6) documentation of efficacy endpoints, 7) data quality issues, 8) flow of forms, and 9) data based protocol modification issues. Following the open session, a closed session will be held. During the closed session, the DSMB chair will conduct a review of all issues and put each issue to a vote. The discussion will focus on treatment safety, efficacy of data, and whether the primary study question has been answered in order to determine when the study data may be released or if an interim analysis is necessary. Following the closed session, an executive meeting may be held to discuss any unmasked analysis of the trial and any sensitive issues surrounding the trial. DSMB recommendations will be made in writing by the DSMB chair to [name].

The secretary will prepare meeting minutes for inclusion in the DSMB report. The report prepared by the DSMB will outline and summarize all discussions during the open and closed sessions of the meeting. The draft report will be reviewed by all Board members prior to issuance of the final report. DSMB recommendations will then be forwarded to the NIH program officer and to the IRB at each study site.

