We are most concerned with the risk of ondansetron exposure to the neonate, although we do not expect significant adverse events attributable to ondansetron compared to placebo (see description of known risk in section 5.0 *Potential Risks*). The Common Rule defines adverse events (AEs) as unanticipated problems. We will use this definition in our reporting and in addition include the potential risks defined in this application. Minor events would include hematoma at phlebotomy site, neonatal rash at electrocardiogram lead sites, or minor maternal side effects mentioned above in section 5.0 *Potential Risks*. We will use the FDA definition of serious adverse events (SAEs) in our reporting. Members of the study team at each site will report AEs and SAEs to [name] and to their local IRB as required at each site. SAEs will be reported within 24 hours of each site's awareness of that event. Within ten working days after receiving a report, [name] will report related AEs and SAEs to the following: Stanford's IRB as the Lead Site IRB, the Data Safety Monitoring Board (DSMB), and the NIH funding institute. He will then follow-up with a written report within 10 working days. The DSMB will determine appropriate action following review of any reported event, and this will be communicated to all study sites, the IRB and NIH funding institute.

Each party (Stanford University as the lead site, and all sub-award sites mentioned in this application) will indemnify for its own negligent acts or omissions. Indemnification will be addressed in the contracts with the sub-award sites, but the specific language is not predetermined, and is therefore not available. The study medication will be subject to normal market warranties for proper manufacturing and labeling.

[name] has applied for an Investigational New Drug (IND) application for ondansetron in neonates to prevent neonatal abstinence syndrome. IND #112007. The application was accepted by the FDA on May 23, 2014, when the Full Clinical Hold was removed for this

protocol. We are proposing a novel clinical investigation that will evaluate the efficacy of a drug for this novel indication. Although [name] has applied for this IND for a new indication of ondansetron, we are not using this data to obtain a new use indication or a label change for this drug from the FDA.

10. Clinical Trials.gov Requirements

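### The adverse event definition leaves out non-serious, foreseeable, unlisted events in neonate and mother, and no by-arm table of adverse events is stated

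*Protocol*

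**What the plan says.** Protocol section 9.0 contains the only AE definition in the two documents. It begins "The Common Rule defines adverse events (AEs) as unanticipated problems" and continues: "We will use this definition in our reporting and in addition include the potential risks defined in this application". Serious events have a separate rule: "We will use the FDA definition of serious adverse events (SAEs) in our reporting". The examples of lesser events are mostly procedural: "Minor events would include hematoma at phlebotomy site, neonatal rash at electrocardiogram lead sites, or minor maternal side effects", the last by reference to section 5.0. Sites report AEs and SAEs to the lead investigator. Onward reports to the lead IRB, the DSMB and the funder are then worded as related AEs and SAEs.

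Three other places rely on the term without redefining it:

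- In section 9.0, the open DSMB session receives the "frequency of adverse events".
- In section 2.1.1, part C, item 7, the contact about 30 days after the last dose asks "if any new adverse events have occurred since the last follow-up call or visit".
- In section 6.2, participants are observed for AEs, and the follow-up calls review them.

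The SAP places dosed infants and mothers in the safety analysis. The only safety test it describes is a two-sample t-test on QTc.

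**The concern.** An AE count is useful in a placebo-controlled trial because it does not require anyone to decide beforehand what the drug might do. Vomiting, loose stools and poor feeding are to be expected in opioid-exposed newborns, and the protocol's own daily questions ask about them. When an event is expected in both arms, only the comparison with placebo can show that the drug makes it more or less common. A definition built on events being unanticipated works against that comparison.

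It matters more here because section 5.0 concedes that neonatal experience with the drug is thin, while section 6.2 asserts that the neonatal risk is no greater than with placebo. Support for that assertion would normally come from a full by-arm event table. For mothers the gap is similar. They belong to the safety analysis, but an ECG is optional for them, so a QTc test cannot carry their safety assessment.

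**Working it through.** The plan has no figure to reproduce; the point turns on a definition.

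**Step 1: what the definition admits.** An event is an AE if it is unanticipated or is a listed risk. An SAE is admitted separately. What falls outside is an event that is non-serious, foreseeable and unlisted.

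**Step 2: how much the list adds.** From sections 5.0 and 6.2:

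| Listed item | Subject |
|---|---|
| QTc abnormality ("If QTc interval abnormalities occur or a neonate has QTcB greater than or equal to 480 ms") | Neonate |
| Delayed onset of NAS | Neonate |
| Haematoma or infection from blood sampling | Mother and neonate |
| Skin irritation from ECG pads | Mother and neonate |
| Ondansetron, neonatal row | No specific event named |
| Ondansetron, maternal row | No specific event named |

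The reference in section 9.0 to minor maternal side effects in section 5.0 therefore leads to a row that lists none for the drug.

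**Step 3: whether another section widens the definition.** The DSMB frequency, the day-30 enquiry and the observation statement in section 6.2 all use the bare term, so they inherit the meaning given in section 9.0. The data lists in sections 4.2 and 4.3 have no AE item.

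**Step 4: what is recorded anyway.** Section 4.3 collects neonatal co-morbidities (item 5), weight change in hospital (item 11), Finnegan scores (item 13), all ECGs (item 14) and feeding (item 15). Section 2.1.1, part C, item 6 provides for daily calls after discharge, for up to 10 days after the last dose, asking about feeding, mood, sleep, vomiting, weight gain and stools; infants still in hospital are checked by daily visits. None of this depends on expectedness. No text labels the answers as AEs or plans to tabulate them by arm as safety events.

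**Step 5: what under-counting could cost (illustration only).** Neither the event rates nor the capture fraction is in the documents; both are assumed. Take a non-serious event at true rates of 10% and 30%, two-sided alpha 0.05, and the same fraction c captured in each arm. With recorded rates p1 = 0.10c and p2 = 0.30c, and their mean p:

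power = Φ{[(p2 − p1) − 1.96·√(2p(1−p)/n)] / √[(p1(1−p1) + p2(1−p2))/n]}

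At n = 45 and c = 1: (0.20 − 1.96 × 0.0843)/0.0816 = 0.425, so power is 67%. At c = 0.5: (0.10 − 1.96 × 0.0632)/0.0624 = −0.384, so power is 35%.

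| Capture | 45 per arm (SAP) | 60 per arm (120 pairs, protocol) |
|---|---|---|
| 100% | 67% | 79% |
| 75% | 51% | 64% |
| 50% | 35% | 45% |
| 25% | 19% | 24% |

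For 20% against 40%, power falls from 55% to 26% at half capture with 45 per arm. The table shows the direction of the loss, not its actual size.

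**The case against.** The strongest reply is that the safety data are largely there. Feeding and weight change, the obvious examples of foreseeable newborn problems, are named data items, and symptoms are asked about daily. This stands. A reader might infer that such events are lost altogether, and the documents do not support that: what is missing is the AE label and a by-arm safety table.

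Second, the definition is stated for reporting, so it could be read as a reporting trigger only. That reading is fair, but no broader definition is written anywhere for the counts given to the DSMB or for the day-30 enquiry.

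Third, some symptoms may come in under the listed risk of delayed NAS. Section 6.2 says the calls review NAS symptoms and other adverse events, which hints that NAS symptoms are themselves treated as AEs. This narrows the gap without closing it, since it does not reach events unrelated to withdrawal.

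Fourth, a reader might infer that a planned AE comparison between arms is made incomplete or biased. The SAP describes no such comparison, and its QTc test does not use the AE definition. Treatment teams are blinded, so any filter on expectedness should act alike in both arms. The likely harm is under-counting and lost sensitivity; the documents show no bias.

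Fifth, variation between sites in what counts as anticipated is plausible with about 5 to 10 sites and no stated criteria, but it is an inference. Reports go to one lead investigator, and the DSMB sets the content of its own reports.

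**Conclusion.** The point holds in a limited form. As written, non-serious, foreseeable, unlisted events in the neonate or mother are not AEs. The AE frequency put before the DSMB and the day-30 enquiry inherit that limit, and no by-arm tabulation of AEs is stated. Serious events, QTc and delayed NAS are covered, and much of the relevant neonatal information is collected under other headings.

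The size of the under-count cannot be derived. A reader might picture an AE table showing no such events in either arm. That would require every site to judge every event expected, and nothing in the documents indicates it. The power figures above rest on assumed rates and on equal capture in both arms. Whether the Common Rule is cited correctly was not judged; the conclusion depends only on the definition the protocol adopts.

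**What to change.** In section 9.0, define an AE as any unfavourable medical occurrence in mother or infant from first study dose to the 30-day contact, whether or not expected or related. Record expectedness and relatedness as attributes of each event. Keep unanticipated and related only as triggers for expedited reporting. In the SAP, state a table of all AEs and SAEs by arm, for infants and mothers separately. That table needs one denominator: the SAP describes its safety population once by receipt of study medication and once, for neonates, by receipt of ondansetron, and the two should be reconciled.

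The SAP is dated March 2022 and written in the past tense, so collection may be complete. In that case, tabulate the recorded symptoms, feeding, weight change and co-morbidities by arm, and state the AE definition used beside any safety claim.

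The prospective change costs protocol wording and somewhat more event recording at contacts already planned. The retrospective one needs only further tables from data the protocol says are collected.

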- a. ECG: The neonate will be stabilized after birth and then will receive a screening 12-lead ECG to rule out QTc Bazett greater than or equal to 480ms. Once the neonate is medically stable and a normal QTc confirmed by the treating physician, the neonate will receive the same 'blinded' study drug (ondansetron or placebo) as his or her mother; this first dose of study drug is to be given between 4-8 hours after delivery. A repeat 12-lead ECG will be done on all neonates following each of the 5 doses of study drug, between 2-5 hours after each dose of study drug. Any neonate that shows significant ECG changes will be excluded from further dosing of study medication but will continue safety follow-up.
 - i. If the QTc is prolonged, the neonate will be transferred to the NICU for continuous cardiac monitoring, if the standard of care indicates the neonate should be admitted to NICU; this will be determined on a case-by-case basis at each site. In addition, a blood test to check the potassium, magnesium, calcium, and ionized calcium levels will be done if the clinical team believe it is necessary for the neonates safety; if the levels are abnormal, electrolytes will be normalized using IV or oral supplements as indicated per standard of care.
 - ii. All ECGs, from all sites, will be sent to Stanford to be interpreted by a cardiologist, who is not a member of the study team, to confirm the accuracy, and consistency of the initial readings.
- b. Standard of Care for Well Baby Nursery:
 - i. Vital Signs: heart rate (HR), respiratory rate (RR), and temperature will be monitored every 4-8 hours depending on the infant's history, and blood pressure at least once per day.
 1. If the HR is less than 80 beats per minute, a rhythm strip or 12-lead ECG is ordered to evaluate the QTc interval, a Neonatal Intensive Care Unit (NICU) physician will assess the neonate and a blood pressure will be obtained.
 2. If the QTc is prolonged, see "ECG" above which discusses the possibility of the neonate being transferred to the NICU for continuous cardiac monitoring if deemed necessary by standard of care
 - ii. A member of the study team will visit the Well Baby Nursery at least once per day to ensure the neonate is doing well and that everyone on the clinical team understands the protocol and knows how to contact the principal investigator to answer questions as needed.

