Interim Analysis: an interim analysis will be performed after a total of twenty (20) pregnant women and their twenty (20) neonates have been enrolled and dosed with study medication. The analysis will include all the ECG measurements, blood concentration levels for pharmacokinetics (PK) and a reassessment of the PK of ondansetron in neonates, all to be reviewed by the DSMB. The study will only proceed if the DSMB gives their approval. These 20 neonates will be the “First cohort” of neonatal patients. (Note, this was done between April and May 2016)

B. Study Medication Dosing

Adult Pregnant Participant’s Dose: The amount and timing of the dose of ondansetron to be administered to the pregnant participants, who are randomized to the ondansetron group, will be 8 mg (IV) within 4 hours of delivery. Should the participant be undelivered 4 hours following the initial dose of study drug, a second dose will be administered. The study medication will be delivered intravenously to the mother prior to either vaginal or cesarean delivery. Exception: if the pregnant participant does not want to receive any study medication prior to delivery because she is not experiencing nausea, she may still continue to be a part of the study and her neonate will be assigned to the study medication she would have been randomized to receive. This allows for an adult patient to not be given the study medication

(ondansetron or placebo) if they feel they do not need it. The neonate's participation will continue as planned.

Neonatal Participant's Dose: The neonates who are born to the mothers, who are randomized to receive ondansetron, will have an initial oral dose of ondansetron 0.07 mg/kg given between 4-8 hours after delivery. The subsequent doses of ondansetron will be 0.07 mg/kg orally every 24 hours for up to 5 doses maximum.

The timing and volume of placebo administration for the 50% of subjects in the placebo group will mimic that of the 50% of subjects in the ondansetron group. Placebo will consist of either normal saline for IV administration or inactive oral syrup for oral administration.

For those neonates who require an intravenous catheter for any other medical reason, these neonates will receive an ondansetron dose of 0.04 mg/kg IV every 24 hours for up to 5 doses maximum.

C. Study Procedures

Adult Pregnant Participant's Procedures:

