9.0 Data and Safety Monitoring Plan

A Data Safety Monitoring Board (DSMB) will be established to ensure the safety and welfare of the subjects enrolled, to ensure the quality of the data, and to make intermittent recommendations whether to continue, modify or stop the trial. The members of the DSMB will be appointed by and report to [name]. The Board members will be independent of the study group. Members will possess expertise in obstetrics, neonatology, addiction, biostatistics, and medical ethics. The Board will also include a public ombudsman, a member from outside of the investigators' institution, and a non-voting secretary, who will keep a written record of every meeting.

DSMB members will disclose in writing to the IRBs of all study institutions any potential conflicts of interest, actual or implied by appearance. At the start of each new member's term, the individual will sign a confidentiality statement promising not to disclose any proprietary and nonproprietary data.

An initial DSMB meeting to discuss the protocol and to establish specific guidelines for monitoring the study will occur before the trial is started. Once the trial commences, interim reports will be sent to the DSMB before each scheduled meeting. The content of the reports will be determined by the DSMB. During the course of the study, any changes to the trial

and/or reporting activities will be made as required by NIH and/or the DSMB.

The DSMB will have discretion to un-blind any results or conduct any inquiry needed to ensure the safety and efficacy of the trial at the request of the DSMB chair. The secretary will maintain a written record of its meetings. Meetings will be scheduled every six months; expedited meetings will be scheduled to review any serious adverse events or adverse events judged by the investigators to be study-drug-related.

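### Protocol section 9.0 promises expedited DSMB review of any SAE but allows ten working days before the DSMB is told, so other neonates could complete a full course first

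*Protocol*

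**What the plan says.** Section 9.0 of the protocol deals with SAEs in two places.

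On meetings, the DSMB convenes every six months, and in between "expedited meetings will be scheduled to review any serious adverse events or adverse events judged by the investigators to be study-drug-related". No time limit is attached to an expedited meeting.

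On reporting, the chain is:

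- Site to lead investigator: "SAEs will be reported within 24 hours of each site's awareness of that event".
- Lead investigator onward: "Within ten working days after receiving a report", the lead investigator "will report related AEs and SAEs to the following": the lead site's IRB, the DSMB and the NIH institute. Serious events have no shorter limit than related non-serious ones.
- Written report: "He will then follow-up with a written report within 10 working days".

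Once the DSMB has reviewed an event, it decides what to do, and that decision goes to all sites.

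Section 6.2 separately requires that a drug-related SAE be reported to the principal investigator, the IRB and the DSMB. It gives no time.

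On neonatal dosing, section 2.1.1 says "this first dose of study drug is to be given between 4-8 hours after delivery" and "The subsequent doses of ondansetron will be 0.07 mg/kg orally every 24 hours for up to 5 doses maximum". Section 6.2 describes "stopping study drug after a maximum of five days of study drug treatment".

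**The concern.** The site step is fast and the next step is slow. An expedited meeting cannot be called about an event the board has not heard of, so the ten-working-day allowance sets the pace of the expedited route.

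This matters at trial level for two reasons. First, the only route the documents state by which other sites learn of the response to an SAE is DSMB action communicated to all of them. Section 2.1.1 expects about 5 to 10 sites. Second, section 2.1.1 blinds the medical and research teams, while section 9.0 lets the DSMB un-blind results. An investigator holding a report would normally be unable to see whether events gather in one arm. The DSMB can find out.

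The protocol itself describes ondansetron as little studied at this age (section 5.0) and names neonatal exposure as its main safety concern (section 9.0). At stake is whether further neonates are dosed while an event awaits forwarding.

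**Working it through.** **1. Length of a course.** The first dose is at 4 to 8 hours, then every 24 hours, with at most five doses (section 2.1.1).

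- Last dose = (4 to 8) + 4 × 24 = 100 to 104 hours = 4.17 to 4.33 days after birth.
- This agrees with the five-day maximum in section 6.2. One screening ECG plus one after each of five doses also gives that section's maximum of 6 ECGs.

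**2. Time to first DSMB notice.** I assume Monday-to-Friday working weeks without holidays.

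- Ten working days = 14 calendar days if the report arrives on a weekday, 13 if on a Saturday, 12 if on a Sunday.
- Adding up to 1 day for the site step: 12 + 1 = 13 to 14 + 1 = 15 days from site awareness. Holidays lengthen this.

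**3. Comparison.** 13 / 4.33 = 3.0 and 15 / 4.17 = 3.6. The permitted delay is about 3.0 to 3.6 course lengths. A neonate born on the day of an SAE at another site could receive all five doses before the DSMB is told.

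**4. Written report.** The protocol does not say when its ten working days start. If they run from receipt, the limit is the same 13 to 15 days. If they follow the first notice, 20 working days is 26 to 28 calendar days, or 27 to 29 with the site step.

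**5. How many others (assumption only).** No accrual rate is stated. With rate r pairs per month and a 15-day delay, expected new pairs = r × 15 / 30.44. Those who could both start and finish fall in a window of 15 − 4.33 = 10.67 days, giving r × 10.67 / 30.44.

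| Assumed pairs per month | New pairs in 15 days | Could start and finish |
|---|---|---|
| 0.85 | 0.4 | 0.3 |
| 2 | 1.0 | 0.7 |
| 4 | 2.0 | 1.4 |
| 8 | 3.9 | 2.8 |

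The lowest rate spreads the first 20 pairs from IND acceptance (23 May 2014) to the interim analysis (April to May 2016), 679 to 739 days, or 0.82 to 0.90 per month. Neither date is an enrolment date. If enrolment started later or pair 20 was enrolled earlier, the true rate for that period was higher. Half of any such pairs would be on placebo.

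**6. Which SAEs are forwarded.** The meeting rule covers any SAE. In the reporting rule, the word related may qualify AEs only, or AEs and SAEs both. On the second reading, SAEs judged unrelated would never reach the board that is meant to review them.

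**The case against.** The strongest reply has five parts.

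- **Ten working days is a ceiling.** The lead investigator may report sooner, and an expedited meeting has no deadline to miss. A meeting after two weeks is still well ahead of a half-yearly one. This stands. A reader might infer that the two rules contradict each other or that expedited review is defeated, and the text does not support that.
- **The affected infant does not depend on the DSMB.** Section 6.2 discontinues study drug for a related SAE. Sections 2.1.1, 2.1.2 and 6.2 stop dosing on the QTc threshold, with an ECG after each dose. This stands for those events, so the short course is not an argument about that infant. It leaves other infants unaddressed.
- **Faster notice does not guarantee action within one course.** Two 24-hour steps take up to 48 hours, and no time to convene is given. This stands. The gain is a board that can start about two weeks earlier, to the benefit of pairs not yet enrolled or dosed.
- **The DSMB's own guidelines may set a faster clock.** Section 9.0 has the board establish monitoring guidelines before the trial starts. They are not in these documents. If they do so, the protocol should say so, because its stated rule is ten working days.
- **The trial may be over.** The SAP, dated March 2022, is written in the past tense. If dosing has ended, the change protects no one in this trial and serves only as a lesson for a successor.

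A reader might also infer from the list of recipients that the FDA is not told of SAEs, although the trial runs under an IND. The list is not said to be exhaustive, and parts of the protocol are not available here, so that inference is not supported.

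**Conclusion.** The point holds as a weakness in the safety reporting chain. The protocol permits about 13 to 15 calendar days from site awareness before the DSMB hears of an SAE, roughly three and a half times a neonatal course at most, with no faster track for serious events. That undercuts the expedited review promised in the same section, without breaking any deadline.

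The exposure falls on other and later neonates. Their number cannot be fixed from the documents. It is below one pair per delay at the slowest assumed rate and about four at 8 pairs per month. The claim that the written report takes up to 29 days rests on reading the two ten-day periods as consecutive, which the text does not settle.

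The conclusion assumes that no unseen DSMB guideline sets a shorter limit. It bears on no endpoint, sample size or analysis. The change is worth making if dosing is still under way, but the trial's validity does not depend on it.

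**What to change.** Reconcile sections 6.2 and 9.0 so that one clock governs SAE notice to the DSMB:

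- The lead investigator forwards every SAE, whether or not judged related, to the DSMB chair within 24 hours of receipt. This matches the scope of the meeting rule and brings the latest first notice from 13 to 15 days down to about 1 + 1 = 2 days after site awareness.
- Ten working days is kept only for the written follow-up, with its starting point stated.
- Section 6.2 refers to that clock.

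The cost is a sentence or two of protocol text and earlier first reports that are less complete, which the written follow-up then fills in. The board would also see SAEs later judged unrelated.
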